### **2. Adverse Events**

For adverse events that are not within the category of serious adverse events, the protocol will be stopped in the events that are 4 adverse event of grade 3 category that are thought to be definitely or probably related to the study protocol. The study will not be stopped for grade 2 or lower adverse events.

## **Blinding and unblinding**

### **1. Blinding:**

- All subjects (including caregivers/companions) and site personnel (including the investigator and study team) will be blinded to the treatment code.
- Individuals who may be unblinded include only the following:
  - Any site personnel for whom this information is important to ensure the safety of the subject in the event of a life-threatening medical emergency
  - Any site personnel for whom this information is important to ensure the safety of the subject and her fetus in the event of a pregnancy
  - Biostatistician preparing the final randomization list
  - MIMDA IDS pharmacy personnel

### **2. Unblinding:**

- At the initiation of the study, the study site will be instructed on the method of breaking the blind.
  - Site investigator to contact site IDS pharmacy personnel
    - In the situation that IDS pharmacy personnel is not available contact the study biostatistician.
  - The unblinder has permission to give verbal or written unblinding to site investigator
- Unblinding of the individual subjects treatment by the investigator will be limited to medical emergencies or urgent clinical situations in which knowledge of the subjects study treatment is necessary for clinical management.
- If a subject's treatment assignment has been unblinded for a medical emergency or urgent clinical situation, the DSMB will be notified within 24 hours of the unblinding event.
- The investigator will consider whether the clinical event that prompted unbinding will be considered an SAE according to the regulatory definitions or criteria for SAEs, and if so, submit an SAE report.
- The reason and the date of the unblinding will be documented clearly in the subjects study file.

## **Unmasking:**

Routine unblinding will occur at the end of the participants V5b visit. The treatment assignment will only be provided to the participant and not the staff at the clinical center. Sealed envelopes with treatment assignment are provided to the clinic to provide the participants.

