Drug return/ Pill counts				*	*		*
Assess for adverse events		*	*	*	*	*	*
Spirometry	*¥	* €				*€	*€
Forced oscillation	*	*				*	*
Lung Volumes	*						
Induced sputum	*					*‡	
Exhaled breath condensate	*	*					*
Exhaled nitric oxide	*	*					*
Methacholine Challenge		*^					*
Nasal lavage & nasal brush	*	*					*
Nasal strip	*	*				*	*
Asthma Control (ACT)	*	*		*	*		*
Marks AQLQ	*	*		*	*		*
ASUI	*						
Anthropometrics	*	*		*	*		*
Temperature	*	*					*
Blood pressure	*	*				*	*
Blood draw†	*	Fasting		Fasting	Fasting	Fasting	
Urine sample	*	*		*	*	*	*
Pregnancy test*	*	*		*	*	*	*
Follow-up phone call			*				
End of study questionnaire							*
Follow-up visit+	*	*				*	*

\*for women of child-bearing potential

¥V1 spirometry only will be performed pre and post bronchodilator

†fasting blood draw may be performed on a different day ( $\pm 7$  days of actual visit)

‡Induced sputum at V5 will be performed within 10 days prior to the other V5 procedures (induced sputum and methacholine cannot be done at same visit, both may cause bronchoconstriction)

^participants with a negative methacholine test will stop visit 2 early

†follow-up visits will be scheduled in the event that a lung test cannot be performed that day

€ spirometry is done as part of the induced sputum or methacholine procedure

∞Visit windows for the visits following visit 2 will be scheduled based off of the date the participant was randomized to study drug

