#### Visit 5a (duration 1.5 hours)

We will schedule the induced sputum prior to other study procedures (within 10 days of V5). We will assess for any adverse events, measure blood pressure, perform forced oscillation, obtain spontaneous sputum or perform the induced sputum procedure, review concomitant medications, and obtain an interim medical history. We will insert a nasal strip for sample collection. We will collect urine for research. Women of childbearing potential will perform a urine pregnancy test. Participants will have fasting blood drawn for

blood glucose, CBC w/ differential, CMP, and collection of serum and plasma for research (this may also be scheduled within 7 days per participant preference).

Visit 5b (duration 3 hours)

We will collect and review diary cards and assess adherence to study medication (by pill count). We will collect all remaining study drug. We will perform nasal lavage, collect nasal cells via nasal brush, measure blood pressure, temperature, obtain weight, and hip and waist circumference. Participants will perform spirometry. We will insert a nasal strip for sample collection. We will collect urine for research. Women of childbearing potential will perform a urine pregnancy test. We will perform a methacholine challenge test with forced oscillation (measuring response by both FEV1 and forced oscillation). If we are unable to obtain sputum from the participant at visit 5a we will see if the participant is able to produce sputum spontaneously during pulmonary function testing. We will collect exhaled breath condensate and exhaled nitric oxide. Participants will complete questionnaires about asthma control and asthma quality of life, and an end of study participant questionnaire.

Additional visit:

Some participants may be asked to return for an additional visit if some of the tests were not completed at the regular scheduled visits or for unexpected events. This additional visit may involve spirometry, a methacholine challenge, or induced sputum depending on the need for the specific participant. The participant's blood pressure will be assessed if the methacholine challenge or induced sputum need to be performed. In addition, women of childbearing potential will be required to undergo a urine pregnancy test prior to testing.

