**Not applicable**

Questionnaires described above will be administered in a private setting at the Vermont Lung Center.

**Statistical Considerations:** *Delineate the precise outcomes to be measured and analyzed. Describe how these results will be measured and statistically analyzed. Delineate methods used to estimate the required number of subjects. Describe power calculations if the study involves comparisons. Perform this analysis on each of the primary and secondary objectives, if possible.*

**Analysis Plan.** Baseline comparability between the two randomized arms will be compared using demographic and outcome variables obtained at baseline to identify potential group comparison confounders. Primary outcomes assessed at the end of the study will be compared using a two-sample t-test and associated 95% confidence interval or a Kruskal-Wallis rank test and nonparametric confidence interval if distributional assumptions are of concern. This will be followed by a pre-post repeated measures mixed linear model to test for group specific baseline to follow-up differences, while for those measures observed at multiple time points, a linear mixed model incorporating time at discrete levels will be implemented. The previous t-test comparisons and the mixed models will be extended to covariance models using baseline mROS, age, sex, BMI, smoking history, duration of asthma and asthma medications, and a confounder score using all items. The effect of medications will be determined by using dummy variables for each class of medication, and by using the cumulative dose of inhaled corticosteroid and  $\beta$  agonist in the regression model. We will compare the rate of events describing any change in medications (whether an increase or decrease), including addition of new anti-asthma drugs and use of steroid tapers in the treatment and placebo groups. Missing data patterns from any lost to follow-up or incomplete data collection will be examined using standard approaches to assess missing at random or missing completely at random assumptions. If missing data is of concern, specific multiple imputation approaches for missing data will be implemented. Analyses using complete data and imputed data sets will be qualitatively compared and presented jointly.

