**Spirometry:**

This is a standard clinical test that may cause discomfort by breathing forcefully through a mouthpiece while wearing nose clips. Occasionally some subjects may feel lightheaded. All testing is done in a seated position under direct monitoring.

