## **Treatment termination:**

Participants may be withdrawn from the treatment if they have a serious adverse event or are intolerant of the treatment per study physician decision. All participants will be asked to return for study visits, until completion of the study.

We will review participants prior history and lung function testing to screen for eligibility, but all procedures will be performed as described in this protocol

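### The participant can learn the treatment assignment before a make-up methacholine test, because unmasking at the end of V5b does not wait for the primary outcome to be completed

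*Combined protocol and SAP*

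**What the plan says.** All references are to the combined protocol and SAP.

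- **Unmasking.** "Routine unblinding will occur at the end of the participants V5b visit". The disclosure is limited: "The treatment assignment will only be provided to the participant and not the staff at the clinical center". The clinic holds sealed envelopes to hand to participants. No condition refers to completed testing.
- **Procedures, Visit 5b.** The methacholine challenge is done at this visit, with response read by both FEV1 and forced oscillation. On study drug: "We will collect all remaining study drug". There is no exception for an outstanding test.
- **Outline of Study Visits, footnotes.** "follow-up visits will be scheduled in the event that a lung test cannot be performed that day". The follow-up row is marked under V1, V2, V5a and V5b, and no window is given for it.
- **Procedures, Additional visit.** Participants may return when tests were missed at their scheduled visits: "This additional visit may involve spirometry, a methacholine challenge, or induced sputum". No latest day is given.
- **Sample size.** The primary outcome is methacholine responsiveness, expressed as the concentration producing a 20% fall in FEV1.
- **Analysis Plan.** "Primary outcomes assessed at the end of the study will be compared using a two-sample t-test". The missing-data text deals with loss to follow-up and incomplete collection. It does not mention tests done late, off drug or after unmasking.

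**The concern.** The trial is double-masked, and its primary outcome is read from a fall in FEV1. The Spirometry risk paragraph describes a forceful breathing manoeuvre, so the value depends partly on participant effort. A participant who has just opened the envelope could try harder or less hard, knowingly or not. That is the influence masking is meant to remove, and the primary outcome is where it matters most.

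Make-up values are also worth protecting. The Sample size section asks for 17 per group. With 40 randomized and 10% drop-out, 18 per arm remain, which leaves one completer per arm to spare on the plan's own figures. If unmasked make-up values were later judged unusable, that margin could be gone. Keeping these values masked costs almost nothing.

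**Working it through.** **Step 1. Trace the order of events for a participant whose challenge is not done at V5b.**

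1. The challenge cannot be done that day. The protocol itself supplies reasons: the Methacholine challenge risk paragraph bars the test for low baseline FEV1 or uncontrolled hypertension, and the Procedures section warns that COVID-19 may delay some procedures.
2. The other V5b procedures go ahead, and all remaining drug is collected (Visit 5b).
3. V5b ends and the envelope is handed over (Unmasking).
4. The participant returns for the challenge (schedule footnote; Additional visit).

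No passage breaks this sequence, and no passage requires it.

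**Step 2. Is the make-up part of V5b or a separate visit?** The follow-up mark sits in the V5b column, which favours treating it as part of V5b. Two places favour a separate visit. The Additional visit paragraph contrasts it with the scheduled visits. Payment for participation sets \$100 for V5b and a further \$50 for each additional visit: the \$500 maximum is already reached by 4 × \$100 + 2 × \$50, so the make-up is paid outside it. The text supports either reading and leans towards a separate visit.

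**Step 3. Illustrate the size.** Inputs from the Sample size section: means of 4 versus 2 mg/ml, SD 3.0 (called within-person), 17 per group, 80% power, 5% level, 10% drop-out, 40 in total. Allocation is 1:1 (Randomization and blinding).

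- Completers, assuming equal drop-out: 40 × 0.9 = 36, or 18 per arm. Margin over the plan: 18 − 17 = 1 per arm.
- Assumption: one MitoQ participant loses a fraction f of the 2 mg/ml gain. Shift in the arm difference = f × 2/18, which runs from 0 (f = 0) to 0.11 mg/ml (f = 1). At f = 1 this is 0.11/2 = 5.6% of the assumed effect.

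To express this in standard errors, the SD must be read in one of three ways. The plan's 17 per group is checked first, using n = 2 × (1.96 + 0.842)² × SD² / 2² (two-sided, normal approximation). Then SE = SD × √(2/18).

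| Reading of 3.0 | SD used | n per group | SE at 18 per arm | 0.11 / SE |
|---|---|---|---|---|
| SD divided by √2 | 2.12 | 17.66, so 18 | 0.71 | 0.16 |
| SD of the compared value | 3.00 | 35.3, so 36 | 1.00 | 0.11 |
| SD of each measurement, changes compared | 4.24 | 70.6, so 71 | 1.41 | 0.08 |

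Only the first reading comes close to the plan's 17, so 0.16 is the figure consistent with the one-spare-completer argument. The shift scales with the number of cases: two give 0.22 mg/ml and three give 0.33 mg/ml. Because effort could also move a value by some other amount, this is an illustration and not a bound. Which SD reading is right is a separate question that does not affect this point.

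**The case against.** **A sensible site would hold the envelope.** The rule concerns routine unblinding and does not address an incomplete V5b, and the follow-up visit is marked in the V5b column. A site could treat V5b as unfinished until its challenge is done, and delay both drug collection and disclosure. The manual of operations named under Data quality, which is not among these documents, may say so. This stands: what is shown is an unspecified order of events, not a planned one. It does not remove the point, because two centres could read the same text differently.

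**The masking that matters most is intact.** Staff are not told the assignment, and on spirometry the protocol says: "All testing is done in a seated position under direct monitoring". The challenge is also read by forced oscillation, which the protocol describes as done while the participant breathes, with no forced manoeuvre. This stands as a real limit. It is not a full answer, because the sample size rests on FEV1 and no passage stops a participant from telling staff.

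**A make-up cannot be very late.** The trial is described as 14 weeks, and V5b falls at week 12 ± 10 days (day 74 to 94). If that window also bound the make-up, the off-drug gap would be at most 94 − 84 = 10 days after a day-84 V5b, or 94 − 74 = 20 days in the extreme. That is plausible, but no passage applies the window to the additional visit.

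**Off-drug values are already accepted.** The Treatment termination section says of participants withdrawn from treatment: "All participants will be asked to return for study visits, until completion of the study". This stands. Being off drug is therefore not the main point; the participant's knowledge of the assignment is.

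**Stronger readings that the documents do not support.** A reader might infer that outcome assessors are unmasked, that the plan intends primary testing after disclosure, that the bias favours MitoQ, or that the drug effect will have worn off by the make-up. Staff masking is explicit. The order is permitted but not required. Effort could change in either direction. No passage says how long any effect lasts.

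**Conclusion.** The point holds and is minor. Followed literally, the unmasking rule allows the primary outcome to be measured in a participant who knows the assignment and has returned the drug, and nothing in the protocol text prevents it. The conclusion rests on reading the make-up as a visit after V5b, which the wording and the payment terms favour without settling.

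The effect per case is small: at most 0.11 mg/ml, or 0.08 to 0.16 of a standard error, for each MitoQ participant assumed to lose some or all of the 2 mg/ml gain. The documents give no expected number of make-ups, so the total effect may be nil. The documents do not support a claim that the trial's result would be materially biased. They support changing the rule, because the weakness is avoidable at almost no cost.

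**What to change.** 1. Amend the Unmasking section so that the envelope is released only after the participant's last outcome test, including any make-up, has been completed or declared missing. This also covers spirometry or forced oscillation made up after V5b.
2. The sponsor should reconcile the collection of all study drug at V5b with the schedule footnote and the Additional visit paragraph, so that both sites handle an outstanding challenge in the same way.

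Optional clarifications: state a latest day for make-up tests, and record the date and the participant's masking status for each one. These are useful detail, but the first change does the main work.

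Cost: one sentence under Unmasking, a short clarification under Procedures, and slightly later disclosure for the few participants who need a make-up. Sample size, visit count and the main analysis do not change.

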## **Treatment termination:**

Participants may be withdrawn from the treatment if they have a serious adverse event or are intolerant of the treatment per study physician decision. All participants will be asked to return for study visits, until completion of the study.

We will review participants prior history and lung function testing to screen for eligibility, but all procedures will be performed as described in this protocol

## DRUG AND DEVICE INFORMATION

*Investigators are encouraged to consult the UVM Medical Center Investigational Pharmacy Drug Service ([name]) prior to finalizing study drug/substance procedures.*

**Drug (s)**

**Not applicable**

*Drug name – generic followed by brand name and common abbreviations. Availability – Source and pharmacology; vial or product sizes and supplier. If a placebo will be used, identify its contents and source. (attach investigational drug brochure)*

**Mitoquinol and placebo** will be supplied by MitoQ Ltd, (based in Auckland, New Zealand).

Name and Product. MitoQ™ (Mitoquinol mesylate) capsules

Active ingredient: Mitoquinol mesylate, inactive ingredients microcrystalline cellulose, tapioca, silica dioxide  
Product will be supplied as 20 mg capsules and matching placebo.

**Methacholine** will be purchased as Provocholine® (methapharm) containing 100 mg in 20 ml vials

*Preparation: Reconstitution instructions; preparation of a sterile product, compounded dosage form; mixing guidelines, including fluid and volume required. Identify who will prepare.*

**MitoQ** Product will be supplied as 20 mg capsules and matching placebo.

**Methacholine** will be reconstituted according to the FDA approved package insert. Dosing of methacholine for this study will be: 0.03125 mg/mL, 0.0625 mg/mL, 0.1250 mg/mL, 0.25 mg/mL, 0.5 mg/mL, 1 mg/mL, 2 mg/mL, 4 mg/mL. Solutions will be prepared using Provocholine® 100mg in 20mL Diluent will be 0.9% Normal Saline.

*Storage and stability – for both intact and mixed products.*

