**Sample size.** The sample size calculations are based upon estimates of clinically meaningful mean differences and standard deviations derived from our studies of obese asthmatics at the University of Vermont (although this is predominantly a Caucasian population compared with the Duke site, we have found that methacholine reactivity variability does not differ by race [or BMI] in prior studies of the ALA-ACRC). The analysis is based upon a repeated measures analysis of variance approach. The primary outcome is the methacholine responsiveness. We assume that after treatment with MitoQ, a 20% fall in FEV1 will be detected using a mean methacholine dose of 4 mg/ml, an improvement over the baseline estimate of 2 mg/ml. It is assumed that those in the control group will show no improvement over baseline. Using a within-person standard deviation of 3.0, and the assumptions indicated above, 17 individuals per group would provide 80% power with a 5% significance level to detect a difference between patients assigned to active treatment versus placebo. We will inflate these numbers to allow for a 10% patient drop-out and plan to recruit 40 participants total. Pre- and post- changes in mean lung function (% predicted) and questionnaire scores will be compared for each group, and across groups as described previously.

**Data quality.** Data Quality will be enforced through a variety of techniques, and in collaboration with [name] in biostatistics at UVM. This includes the preparation of a detailed manual of operations, staff training and certification of key staff in study procedures, design of unambiguous self-documenting data collection forms, double data entry, audit of source documents against the central database, automated intra-form and inter-form data consistency checks, range and validity checks during data entry, and centralized eligibility checks and randomization assignments. We will have an in-person training meeting at the start of this clinical study for the Investigators and Coordinators at Duke and UVM.

Data quality will be reviewed and discussed at monthly conference calls. [name] will meet in person no less than three times a year at the Steering Committee meetings of the American Lung Association-Airways Clinical Research Center network.

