**Inclusion criteria:**

1. participant reported physician diagnosis of asthma
2. participant reported on regular prescribed controller therapy for at least 3 months
3. positive methacholine challenge (as determined by spirometry PD20 or oscillometry PD50 ≤ 4.0 mg/ml at visit 2)
4. age: ≥18 years
5. BMI ≥ 30 kg/m^2 (at visit 1)
6. poorly controlled asthma defined as one of the following:
  - a. Asthma Control Test Score ≤ 19 (at visit 1), or
  - b. Participant reported use of rescue inhaler on average > 2 uses/week for preceding month, or
  - c. Participant reported nocturnal asthma awakening on average 1 or more times / week in preceding month, or
  - d. Participant reported ED/hospital visit or prednisone course for asthma in past six months
7. ability and willingness to provide informed consent

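### The methacholine ladder stops at the treated mean assumed for sample size, no analysis value is given for a result above it, and the plan does not settle on one primary analysis

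*Combined protocol and SAP*

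**What the plan says.** - **Ladder.** Drug and Device Information, methacholine preparation, lists one set of doubling concentrations from 0.03125 mg/mL, ending "0.5 mg/mL, 1 mg/mL, 2 mg/mL, 4 mg/mL".
- **Entry.** Inclusion criterion 3 requires a "positive methacholine challenge (as determined by spirometry" or by oscillometry, at or below 4.0 mg/ml at visit 2. Either measure is enough.
- **Sample size.** A 20% fall in FEV1 after MitoQ "will be detected using a mean methacholine dose of 4 mg/ml, an improvement over the baseline estimate of 2 mg/ml". For placebo: "It is assumed that those in the control group will show no improvement over baseline". The calculation proceeds "Using a within-person standard deviation of 3.0, and the assumptions indicated above" to 17 per group for 80% power at the 5% level, and 40 in total after 10% drop-out.
- **Negative test.** The visit table has one footnote: "participants with a negative methacholine test will stop visit 2 early". This concerns eligibility. Nothing is said about the same result at visit 5b.
- **Which analysis.** Primary Outcome names change in airway reactivity. The Analysis Plan lists first a t-test on primary outcomes at study end, or a rank test if distributions cause concern. A pre-post mixed model comes next, then covariate-adjusted versions. The covariate list does not name the baseline methacholine value. The Sample size section says: "The analysis is based upon a repeated measures analysis of variance approach".
- **Missing data.** The Analysis Plan covers loss to follow-up and incomplete collection. A completed challenge with no 20% fall is neither.

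**The concern.** One number serves as the measurement ceiling, the entry limit and the hoped-for treated average. A treatment that works pushes participants above the ceiling, where the test no longer says how far they improved. Entry on oscillometry alone may also admit people who are already '>4' on FEV1, so the gap can affect baseline too.

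Three things are at stake: power; an effect size that does not depend on an arbitrary code; and, if test and code are chosen after seeing results, control of the false-positive rate. The effect size matters here because Study Design says the findings will inform a decision on a full-scale trial.

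**Working it through.** **1. The plan's sample size.** Inputs from the Sample size section: difference 4 − 2 = 2 mg/ml, control change 0, SD 3.0, 17 per group, 80% power, 5% (two-sided assumed). For a two-sample t-test, power = P(|T| > t(0.975, 2n−2)), where T is noncentral t with λ = (2/SD)·√(n/2). At n = 17, √(17/2) = 2.92.

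| SD of change | λ | Power at 17 per arm | n per arm for 80% |
|---|---|---|---|
| 2.0 | 2.92 | 81% | 17 |
| 3.0 | 1.94 | 47% | 37 |
| 4.24 (= 3.0·√2, if 3.0 is the SD of one reading) | 1.37 | 27% | 72 |

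The stated 17 is not reproduced for active versus placebo at either reading of 3.0. The one near match with SD 3.0 is a paired or single-group normal approximation: (3.0 × (1.960 + 0.842)/2)² = 17.66. That is not the stated contrast. If 3.0 were the SD of a single measurement, an SD of change of 2.0 would need a pre-post correlation of 1 − 4/18 = 0.78, which is not stated. The drop-out step is fine: 34/0.90 = 37.8, so 40 covers it and leaves 36, or 18 per arm.

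**2. The ceiling against the assumed effect.** If '>4' is recorded as 4, no value exceeds 4. A treated mean of 4 with control at 2 then requires every treated participant to be at the top step. If values are not capped and the treated mean is 4, the share above the top step is 50% for a symmetric distribution and about 34–41% for a lognormal with an assumed CV of 1.0 to 0.5.

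**3. Effect of the missing rule.** The documents give no usable spread, so all distributional inputs here are assumptions. Main case: 18 per arm; true log2 value normal with mean 1.5 and SD 1.2; SD of change 1.0 doubling (per reading 1.0/√2); entrants have a measured baseline at or below 4, which gives a mean of 1.9 mg/ml; true effect one doubling; 4000 runs, Monte Carlo error at most 0.8 points.

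- Result '>4' at the end: 48% active, 17% placebo.

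| '>4' entered as | Observed difference, mg/ml | Baseline-adjusted log2 estimate, doublings (true 1.0) |
|---|---|---|
| 4 | 0.96 | 0.69 |
| 8 | 2.19 | 1.00 |
| 16 | 4.66 | 1.31 |

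A second run of the main case gave 4.61 for the last difference. A censored log2 model gives 0.99–1.02 for a true 1.0 over ten cases (three SDs by two baseline levels, two with oscillometry-only entrants, two with no drift in controls).

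**4. Effect of the choice of analysis.** Power with '>4' coded 4, except the last column:

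| SD of change | End-of-study t-test | Raw change | Adjusted log2 | Adjusted log2, coded 8 |
|---|---|---|---|---|
| 0.75 | 75% | 93% | 94% | 96% |
| 1.0 | 67% | 75% | 80% | 83% |
| 1.4 | 50% | 49% | 54% | 58% |

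A repeat of the main case gave 65%, 75% and 78–83%. The rank test is close to the t-test (66%). With complete data, raw change is the same test as a between-arm pre-post mixed model. Over the ten cases, adjusted log2 coded 8 gains 8–27 points over the end-of-study t-test and 2–16 over raw change.

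**5. False positives.** Each single test, fixed in advance, runs at 4.0–5.7%. Taking the better of t-test and rank test at one code gives 5–7%. With the code (4 or 8) also open, 7–8%. With the change test open as well, 10–14%.

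**The case against.** **The analysis plan has an order.** The t-test comes first and the mixed model follows, so the t-test could be read as primary. The pre-post model uses the baseline value, and the plan opens by comparing outcome variables between arms at baseline. This stands in part: baseline is not ignored. But the first-listed test most naturally leaves it out, and that conflicts with an outcome defined as change and a size based on repeated measures. A comparison of change is a possible reading of the first test; the plan should say so if it is meant.

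**A reader might infer a false-positive rate of 10–14%.** The documents do not support that as the plan's error rate. It is an upper bound that needs free choice of both code and change test, despite the stated order. The switch the plan leaves open gives 5–7%. The mixed-model sentence can also be read as testing change within each arm.

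**A reader might infer that an SD of 3.0 is impossible on this ladder.** Two values between 0.03125 and 4 have a within-person SD of at most 3.97/√2 = 2.81. But that bound needs 3.0 to be in raw mg/ml and results capped at 4. The plan states no scale, and it takes the SD from earlier studies whose ladder is not given.

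**A reader might infer that no rule exists anywhere.** The Data quality section promises "the preparation of a detailed manual of operations", which was not supplied, and a short part of the document was not available. A rule may be there; if so, it belongs in the plan.

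**The main case is near the high end for censoring.** True: active-arm '>4' runs from 27% to 49% over the six cases that vary SD and baseline level. Needing every treated participant at 4 also depends on control staying at 2, as the plan assumes; with control at about 1.4, a treated mean of 3.4 would give the same difference.

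**Conclusion.** The point holds. 4 mg/mL is the top step, the entry limit and the assumed treated mean; the supplied text gives no analysis value for '>4'; and three sections describe three analyses of the primary outcome.

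The firmest consequence is for the effect size: under the main-case assumptions the same trial would report about 1.0, 2.2 or 4.6 mg/ml depending on an unwritten code. The power loss is clear against the end-of-study t-test. Against the plan's own pre-post comparison it is modest: 5–8 points in the main case and 5–9 at an SD of change of 1.4, where no analysis in the table reaches 60%. Power loss over the pre-post comparison would not carry the point alone.

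It would be wrong to call the planned tests invalid. Randomisation protects any one of them if it and the code are fixed beforehand.

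The sample-size discrepancy is separate and does not rest on the simulation: 17 per group does not give 80% power for active versus placebo if 3.0 is the SD of change (47%) or of one reading (27%). It assumes a two-sided test and 3.0 on the same scale as the difference of 2.

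**What to change.** 1. **Define '>4' before unblinding.** A completed challenge with no 20% fall at 4 mg/ml is a result, at baseline and at the end; it is not missing and not imputed. A challenge not done is missing, with the reason recorded. The Methacholine challenge risk section bars the test below an FEV1 threshold, so participants who worsen may have no value; add a sensitivity analysis for tests not done for that reason.
2. **Name one primary between-arm analysis.** Use end-of-study log2 methacholine concentration, adjusted for baseline log2 value and centre, with one prespecified handling of '>4'. Either use a censored log2 model, with p-value and confidence interval by within-centre re-randomisation (its ordinary likelihood-ratio test ran at 6–7%), or a fixed analysis code with a sensitivity range. Take the effect size and p-value from the same model. Add an indicator for baseline '>4' only if there are enough such participants.
3. **Remove the data-driven switch** between t-test and rank test, and label the other models supportive. Add a baseline-adjusted rank analysis with all '>4' tied at the top as sensitivity.
4. **Restate the sample size.** Give the effect and SD on the analysis scale, say which SD is meant, and state the power that 40 participants deliver.
5. **Reconcile** Primary Outcome, Analysis Plan, Sample size, the methacholine ladder and inclusion criterion 3. No methacholine dose is proposed here.

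**Cost:** plan wording and a little code. Results will be in doublings rather than mg/ml. The estimate will rest on a censoring model or a code; a fixed code of 8, for example, gave 0.83–1.07 for a true 1.0 and 1.37 for a true 1.5. The restated power may fall below 80%.
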